- c. problem-solving Variable: IGDI problem-solving score
- d. global development Variable: Bayley III score

Hypothesis 2: Compared to the BAU group, the START-Play group will show greater sustained improvements from pre-intervention to one year since start of intervention (long-term effect) in:

- a. sitting Variable: Gross Motor Function Measure (GMFM) sitting scores
- b. reaching Variable: Number of toy contacts
- c. problem-solving Variable: IGDI problem-solving score
- d. global development Variable: Bayley III score

Hypothesis 3 (Mediation): Improvements in global development will be (at least) partially mediated by improvements in problem-solving as a function of the intervention at the end of the project (long-term proximal effect).

Variables: GMFM scores, toy contacts, IGDI problem-solving and Bayley III scores.

SECONDARY HYPOTHESES

Analysis of moderators

1. *Hypothesis:* Severity of motor impairment will have a significant influence on overall change in IGDI problem-solving, and motor scores, as well as Bayley III scores. Variable: Severity score (see Table 1)

2. *Hypothesis:* Factors external to the child (socialization opportunities [Modified Parent Child Interaction-Dyadic Mini Code scores (Censullo, 1991) (PCI-DMC)], and home environment (HOME Inventory [Bradley, 1993] & SES), will have a moderate effect on change in GMFM, problem-solving, and Bayley III scores.

Further analysis of motor variables

3. *Hypothesis:* The START-Play group will show posture control measures that are closer to normative values than the BAU group from pre to post intervention. This hypothesis tests additional variables quantifying sitting to supplement Primary Hypothesis 1. Variables: Kinematic measures taken from video analysis.

4. *Hypothesis:* Compared to the BAU group, the START-Play Intervention group will show greater improvements in duration of toy contact and object manipulation from pre to post intervention. This hypothesis tests additional variables quantifying reaching to supplement the

Primary Hypothesis 2. Variables: Unilateral and bilateral contact number and duration, and type of contact (i.e. hand open or closed; palmar or dorsal hand surface, manipulation variables).

iii. Research Design

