	Business-as-usual*	START-Play	Difference
Frequency	Once weekly to once monthly	Twice weekly	Increased frequency of interaction
Intervention Model	Transdisciplinary or interdisciplinary- may be teacher, PT, OT or Speech	Short term focus with expert in motor (physical therapist) in partnership with parent for activities below (Appendix C)	Increased focus for caregiver on understanding motor and linkage to problem-solving
Content of Session	Directed to Parent: (25%) 
 • Parent Training 25% Directed to Child: (55%) 
 • Task Guidance w/ PT 25% • Postural Control & Strengthen w/ PT 20% • Tolerate Positions 10% • Equipment/Stretch w/ PT 10% 	Directed to Parent: (35%) 
 • Analysis with parent & setup 20% • Parent-led activity 15% Directed to Child: (40%) 
 • Child-led activity with sitting /reaching 25% • Expand child-led activity - variability 15% Readiness to learn related: (25%) 
 • Link motor acts to problem-solving and cognition 25% 	Parent/caregiver taught all aspects, not just tasks, but also the “why” behind the action, connections to previous and later skills, problem-solving links, cognitive outcome expected for each action

	Readiness to learn related: (10%) • Cognitive - < 10%		
Example Content	
 1. Practice sitting balance reactions on a ball (isolated motor task) 2. Therapist provides supportive seat to constrain trunk, and suggests presenting toys on tray in front of infant and modeling use of toy 	
 1. Select activity for motor based problem solving – finding hidden toy. Child encouraged to shift weight, re-orient to look behind/under/in containers, thus building sitting balance in the service of spatial understanding 2. Dynamic low support sitting allows child to re-orient and gain spatial understanding; multiple options for variable sitting support depending on problem-solving task. 	
 1. Cognitive construct is selected first and is primary; movements are built around the cognitive construct 2. Parents taught that chair is passive and not variable. Multiple options, with minimal support needed, allow exploration and link motor to problem solving

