A parallel process growth modeling approach as implemented in the SEM framework will be used to simultaneously address the remaining primary research hypotheses: (3) improvements in sitting and reaching as a function of the intervention will be associated with increases in global development at the end of the project (long term effect); and (4) improvements in global development will be (at least) partially mediated by improvements in problem solving as a function of the intervention at the end of the project (long-term effect). Because the global development and problem solving constructs occur over time and are characterized as improvements (i.e. changes), we consider the mediational model as a SEM (see simplified model in Figure 1) that allows multiple simultaneous direct and indirect paths while modeling growth (Cheong, 2003). This approach will allow us to assess possible mediating effects of improvements in sitting, reaching, and problem solving through the intervention period (RX) on the relationship between intervention participation (START-Play) and improvements in global development through the one-year follow-up (LT). This model will be evaluated for the significance and directionality of included path coefficients and overall model fit. It is expected that the indirect effect of the intervention (derived by tracing solid paths $A*B$, and $A*C_1*C_2$) on child outcomes will be statistically significant and the direct effects of the intervention (dashed path D) will also remain significant, thus demonstrating partial mediation. Hypothesis 3 will be evaluated by comparing the magnitude of the $A*B$ indirect effect to the direct effect, D. Hypothesis 4 will be evaluated by comparing the magnitude of the $A*C_1*C_2$ indirect effect to the direct effect, D. Partial mediation is an appropriate hypothesis as the intervention is expected to have a substantial effect on problem solving, but there are other factors beyond problem solving, sitting and reaching that contribute to improvements in global development that are represented by the direct effect. By hypothesizing that assignment to condition (START-Play) leads to proximal changes in the mediator(s) (RX) which then lead to distal effects in the outcome (LT), we also meet the requirement of temporal precedence necessary for strong mediational inferences.

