Evaluation of Secondary Hypotheses 1 & 2: Improvements in sitting, reaching, problem-solving and global development will be moderated by (1) internal variables: the severity of neuromotor disorder, health status, entry age, cognitive status at entry; and (2) external variables:

Figure 2. Mediated Effects Model for Hyp. 3 & 4

Note: RX = intervention phase; LT = follow-up phase; START-Play = assignment to condition; A,C = direct effects of the intervention on proximal & distal outcomes, B₁ & B₂ = effect of mediator(s) on other outcomes

socioeconomic status, compliance/attendance to home visits, the home environment (HOME), and overall amount of service to the family and child. Evaluation of these variables as moderators of the effect of the intervention on change in primary outcomes (sitting, reaching, problem solving and global development) will be done by modifying the LMM model equation used in evaluation primary hypothesis 2. Two three-way interaction terms, $TRT_{0i}RX_{it}MOD_{1i}$ and $TRT_{0i}LT_{it}MOD_{1i}$, where MOD_{1i} represents an individual moderator, will be added to the model to capture the intervention by time by moderator interaction. The simple effect of the moderator, MOD_{1i} , will be included as well as relevant 2-way interactions. All continuous variables will be mean-centered prior to forming cross-product interaction terms, and all categorical variables will be dummy coded prior to forming interaction terms. Each potential moderator will first be entered individually, and later in combination, with each primary outcome tested separately.

Evaluation of Secondary Hypothesis 3: Relative to infants in the BAU group, infants in the intervention group will show greater improvements in sitting control both post-intervention and at long-term follow-up. Evaluation of this secondary hypothesis will utilize the same LMM framework presented for evaluating primary hypotheses 1 and 2, with the exception that the outcome measures will be trunk forward bending, angular displacement, and velocity of trunk.

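### Mediation by problem-solving, the listed Primary Hypothesis 3, is renumbered in the analysis section and judged only on the part of the effect routed through sitting and reaching

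*SAP*

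**What the plan says.** **Listed hypotheses.** Protocol section 1 and SAP section ii name three primary hypotheses. The third reads "Improvements in global development will be (at least) partially mediated by improvements in problem-solving as a function of the intervention". Beneath it stands "Variables: GMFM scores, toy contacts, IGDI problem-solving and Bayley III scores".

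**Analysed hypotheses.** SAP sections iv and ix power and analyse four. In section ix, number 3 is that "improvements in sitting and reaching as a function of the intervention will be associated with increases in global development", and "Hypothesis 3 will be evaluated by comparing the magnitude of the $A*B$ indirect effect to the direct effect, D". Number 4 is that "improvements in global development will be (at least) partially mediated by improvements in problem solving as a function of the intervention", which is the listed third hypothesis, and "Hypothesis 4 will be evaluated by comparing the magnitude of the $A*C_1*C_2$ indirect effect to the direct effect, D".

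**Theory.** SAP section viii describes a serial chain: motor skill affects problem-solving, which affects global development. Its four mediation steps follow that chain.

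**Program content.** Protocol section 1 names problem-solving as a target beside sitting and reaching. SAP Table 4 gives 25% of a START-Play session to linking motor acts with problem-solving and cognition, and says of its example content: "Cognitive construct is selected first and is primary; movements are built around the cognitive construct". Section ix expects a substantial intervention effect on problem-solving. Section iv assumes d = 1.11 for it.

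**Path labels.** The text uses A, B, C1, C2 and D. The Figure 2 note uses A, C, B1 and B2, and says "A,C = direct effects of the intervention on proximal & distal outcomes". The text points to Figure 1 for the model, while the caption says Figure 2.

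**The concern.** The listed hypothesis is about mediation by problem-solving as a result of the intervention. It is not restricted to problem-solving gains that arise from better sitting or reaching. The stated rule counts only those gains. No product of the form START-Play to problem-solving to global development is named.

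Two things are at stake. First, if START-Play improves problem-solving partly by training it, that part is missing from the indirect effect reported for a primary hypothesis. A null serial product could then be read as no mediation by problem-solving. Second, if the fitted model has no START-Play to problem-solving path, the whole arm difference in problem-solving has to pass through motor change. C1 then absorbs part of the direct effect, and the trial could report a motor-to-cognition chain that is weaker than claimed or not there.

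The numbering adds a separate difficulty. The motor hypothesis carrying the number 3 in section ix is not among the listed primary hypotheses, so a reader matching by number alone would be sent to a product without problem-solving in it.

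**Working it through.** **1. Numbering, side by side**

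| Place | Number 3 | Number 4 |
|---|---|---|
| Protocol 1, SAP ii | mediation by problem-solving | not listed |
| SAP iv (power) | path B | C1×C2 |
| SAP ix | motor to global development, A×B | mediation by problem-solving, A×C1×C2 |

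**2. What the products mean.** A is common to both. A×B belongs to the motor hypothesis, so A ends at sitting/reaching and B runs from there to global development. C1×C2 then runs from sitting/reaching through problem-solving. Section iv takes only A and D from the group differences. This reading is inferred from the text, because the figure is not shown.

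**3. The plan's own figure.** Section iv gives 80% power for a standardized coefficient of .237. The SEM power run cannot be rebuilt, as path values and variances are not given. A Fisher-z proxy for a single coefficient is Φ(atanh(.237)×√(N−3) − 1.96): .839 at N = 152 and .807 at N = 140. That is in the neighbourhood of 80%. The point here does not rest on it.

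**4. Path fitted, only the serial product reported.** Let E be the direct START-Play to problem-solving effect. Convert d by r = d/√(d²+4): sitting 1.21 gives A = .518, and problem-solving 1.11 gives a total effect of .485. The motor-routed share is .518×C1/.485. C1 is not given, so a range is shown. The power columns are simulated at N = 140 with joint-significance tests, assuming C2 = .30, B = .10, D = .05.

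| C1 | Motor-routed share | Power, A×C1×C2 | Power, total problem-solving route |
|---|---|---|---|
| 0 | 0% | 5% | 91% |
| .10 | 11% | 19% | 91% |
| .237 | 25% | 73% | 90% |
| .487 | 52% | 83% | 83% |

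At C1 = 0 the 5% is a false-declaration rate. The share reaches 100% only at C1 = .485/.518, about .94.

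**5. Path not fitted.** Unit residual SDs, 1:1 allocation (arm variance 0.25), A = 1.21, C2 = 0.3:

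- Fitted C1 = C1 + E×A×0.25/(A²×0.25 + 1) = C1 + 0.221×E, since 0.3025/1.366 = 0.221.
- Captured share = A×(fitted C1)/(E + A×C1).

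| True C1 | E | Fitted C1 | Captured share |
|---|---|---|---|
| 0 | 1.11 | 0.246 | 0.297/1.11 = 27% |
| 0.1 | 0.45 | 0.200 | 0.242/0.571 = 42% |
| 0.237 | 0.823 | 0.419 | 0.507/1.11 = 46% |
| 0.3 | 0.3 | 0.366 | 0.443/0.663 = 67% |

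In the first row the reported product is 1.21×0.246×0.3 = 0.09. The true chain is 0 and the true problem-solving-mediated effect is 1.11×0.3 = 0.33. Simulated at N = 140 with joint significance of A, C1 and C2, the chain is declared in about 81% of trials without the path and about 5% with it. In the last row the figures are about 93% and 87%, so there the omission changes the declaration little.

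**6. Effect on D.** In the first-row setting without the path, fitted D averaged 0.005 at true D = 0 and 0.193 at true D = 0.20. D comes from the global-development equation, which already conditions on arm, motor change and problem-solving.

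**7. Would the fit check catch an omitted path?** In the first-row setting the misfit is ln(1 + E²×0.25/1.366) = ln(1.2255) = 0.203. Spread over the SAP's 115 df, RMSEA = √(0.203/115) = 0.042, inside its close-fit limit of 0.05.

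**The case against.** The best defence is that the serial path is the stated theory. SAP section viii defines mediation that way, the motor measures are listed under Hypothesis 3, and protocol sections 3 and 8 describe problem-solving as improving secondarily to, or by way of, sitting and reaching. Section ix also restates the listed hypothesis in nearly the same words before assigning it A×C1×C2, so a careful reader would not be misled by the number. All of this stands. A reader might infer that the listed hypothesis is not tested at all. The documents do not support that, because A×C1×C2 passes through problem-solving and a significant result would support partial mediation.

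The figure is also missing. Section ix calls the model simplified and says it allows several direct and indirect paths, so a START-Play to problem-solving arrow may exist. If it does, inflation of C1 and false declaration of the chain do not arise. What remains is that the stated decision rule leaves that route out.

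A reader might also infer that the omitted mediation is credited to the direct effect D. Step 6 shows it is not: the omitted part drops out of the decomposition.

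Finally, this is a mechanism analysis. The arm comparisons under Hypotheses 1 and 2, including the effect on problem-solving itself, are untouched.

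**Conclusion.** The point holds as one of incomplete coverage and inconsistent labelling. The problem-solving hypothesis is judged on the serial component alone, while the documents give reasons to expect a direct component. The numbering conflict and the clash of path letters are plain on the page and do not depend on the missing figure.

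The size is illustrative. E, C1 and C2 are assumptions, and the calculations use observed variables with one motor mediator, not the planned parallel-process growth model. The 81% against 5%, and the 27% captured, need both an unfitted path and no true motor effect on problem-solving, which is contrary to the SAP's own theory. They should not be read as the expected error rate of this trial. With C1 of 0.1 to 0.3 and smaller direct effects, 42% to 67% is captured in the settings tried. The direction is the same for any positive E and C2. This should be fixed before analysis, but it does not threaten the trial's main comparisons.

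**What to change.** - State whether the parallel-process SEM contains a START-Play to problem-solving slope path (E). If not, add it.
- Judge the listed Hypothesis 3 on the total indirect effect through problem-solving, (E + A×C1)×C2, with a bootstrap confidence interval. Report A×C1×C2 as the serial component that answers SAP section viii.
- Use one hypothesis numbering across protocol section 1 and SAP sections ii, iv and ix. Either list the motor hypothesis (A×B) as primary or label it exploratory.
- Use one set of path letters in the text, the power section and the figure note, and correct the figure reference.

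The cost is SAP wording and at most one extra model parameter. No new data are needed.

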- **iv. Power**
- Sample Size: Each of the 4 sites will recruit 38 infants (total $N=152$) to retain 35 infants for a total of $N = 140$ infants in the study. The initial ($N=152$) and retained ($N=140$, $n=70$ per condition) sample sizes were chosen according to feasibility of recruitment in each site as well as considerations of time and resources needed for a 4-year study.
- Power analysis for Primary Hypotheses 1 & 2: We used a simulation-based power analysis (Muthén & Muthén, 2002; Theommes et al, 2010) to estimate the power for the randomized trial with repeated measures design as evaluated with the proposed Linear mixed modeling (LMM; Laird & Ware, 1982; Wallace & Green, 2002) utilizing FIML for attrition-based missing data. *Mplus* was used for simulations and empirical analyses. Simulations were based on detecting significance in the treatment by time interaction during the intervention phase, γ_{11} . The analysis assumed a small intraclass correlation for the slope across infants (e.g., small variance of the treatment effect of 0.05; Raudenbush & Liu, 2000), a two-tailed nominal error rate of $\alpha = .05$, an initial sample size of 152 infants at baseline, and an attrition scenario of 10% loss by the end of the 3-month intervention (based on patterns observed in previous research conducted by the collaborative team). We conducted the power analysis essentially in support of Hypothesis 1 (the short-term effect at the end of the intervention phase) based on the position that Hypothesis 2 will be supported if the initial effect is then at least sustained through the follow-up period which would be evidenced by a non-significant γ_{21} parameter (no differential change). Prior published research by [name] et al. (2010) and Heathcock et al. (2008) were used to derive effect size estimates for sitting (GMFM, $d=1.21$) and reaching (toy contacts, $d=1.32$), respectively. Pilot data from [name] & [name] and [name] were used to derive

effect size estimates for global development (Bayley III, $d=0.43$) and problem solving (IGDI, $d=1.11$), respectively.

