assessed for the full potential of information. Appropriate error-rate control is discussed in a later section. Severity of neuromotor disorder (stratification variable) and fidelity of implementation will be added as covariates, and child-level characteristics, such as gender and ethnicity, also may be included in the analysis as child-level covariates. Due to the small sample size ($J = 4$) and the convenience sampling of sites involved in the study, site will be included as a *fixed* classroom level effect rather than an additional hierarchical level or random effect. Our analytic model is presented as a piecewise LMM where Y_{it} is the outcome variable score at time t for child i , TRT_{0i} is a contrast variable denoting the intervention status for child i (i.e., 0=BAU, 1=START-Play), RX_{it} is the passage of time during the intervention phase of the study from baseline to the end of the third month, and LT_{it} is the passage of time from the end of intervention through one calendar year since entering the study. While presented here as linear effects within each study phase (RX and LT), we will also explore any potential curvilinearity as well. The second line of the equation reflects the remaining fixed covariate effects ($CTRL_{0i}$ =neuromotor disorder severity, fidelity;

COV_{0i} =child covariate [i.e., gender]; and S_{0i} =site). *The model can be expanded to consider additional covariates*

$$Y_{it} = \gamma_{00} + \gamma_{01}TRT_{0i} + \gamma_{10}RX_{it} + \gamma_{20}LT_{it} + \gamma_{11}TRT_{0i}RX_{it} + \gamma_{21}TRT_{0i}LT_{it} + \gamma_{02}CTRL_{0i} + \gamma_{03}COV_{0i} + \gamma_{04}S_{0i} + u_{0i} + u_{1i}RX_{it} + u_{2i}LT_{it} + \varepsilon_{it}$$

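### As described, the mediation model adjusts the mediator-to-outcome paths for no baseline factor, although the SAP itself expects severity to influence change in both mediator and outcome

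*SAP*

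**What the plan says.** SAP section ix (Evaluation of Primary Hypotheses 3 & 4) specifies a parallel process growth SEM. Treatment acts on change in the mediators during the intervention phase (RX) through path A. The mediators act on improvement in global development through follow-up (LT) through B, or through the chain C1 and C2. D is the direct effect of treatment. The model is judged on the significance and direction of its paths and on fit, and each hypothesis by comparing its indirect effect (A×B or A×C1×C2) with D. D is expected to remain significant.

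No covariate is named for this model. The causal argument is that by placing mediator change before outcome change "we also meet the requirement of temporal precedence necessary for strong mediational inferences". On remaining influences the SAP says that "there are other factors beyond problem solving, sitting and reaching that contribute to improvements in global development that are represented by the direct effect".

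Elsewhere in the SAP:
- Section ii, Secondary Hypothesis 1: "Severity of motor impairment will have a significant influence on overall change in IGDI problem-solving, and motor scores, as well as Bayley III scores".
- Section ii, Secondary Hypothesis 2: parent-child interaction, HOME and SES "will have a moderate effect on change in GMFM, problem-solving, and Bayley III scores".
- Section ix, model for Hypotheses 1 and 2: "Severity of neuromotor disorder (stratification variable) and fidelity of implementation will be added as covariates". Site is also included. The printed equation enters these as level terms, with no covariate-by-time term.
- Section viii lists four steps for showing mediation, again with no covariate.

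The path figure is not shown in the text available, and the SAP calls it simplified. Section ii numbers the problem-solving mediation as Hypothesis 3; section ix numbers it 4.

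**The concern.** Path A starts at a randomised variable. Paths B, C1 and C2 do not: they relate one child's observed change on one measure to the same child's change on another. If a baseline characteristic influences both changes, the two are correlated within arm even when neither affects the other. Testing B = 0 without that characteristic tests for no within-arm association, which is not the same null as no effect of the mediator.

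On the SAP's own prediction, severity is such a characteristic. Timing does not help, because severity at entry precedes both mediator and outcome. Nor can D absorb it: D is the coefficient on arm, and a baseline factor independent of arm stays in the mediator-outcome association.

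At stake is the trial's theory of change. Path A is expected to be strong (d = 1.21 for sitting, 1.11 for problem solving in SAP section iv), so a claim of mediation turns largely on B, or on C1 and C2.

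**Working it through.** **Inputs from SAP section iv.** Two-sided alpha .05 (stated for Hypotheses 1 and 2, assumed here for the SEM paths); "an initial sample size of 152 infants at baseline, and an attrition scenario of 10% loss by the end of the 3-month intervention", so 152 × 0.9 ≈ 137 analysed; d = 1.21 for sitting (path A) and 0.43 for Bayley III; 80% power at a standardised mediator path of .237.

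**Assumed, because the documents give no figure.** The share of variance in each change score that severity explains, R²m for the mediator and R²y for the outcome, and its direction.

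**1. The plan's own figure.** Power for a standardised path is approximately Φ(atanh(.237) × √(N − 3) − 1.96). This gives 83.9% at N = 152, 80.7% at N = 140 and 79.9% at N = 137. The stated 80% is reproduced once attrition is applied.

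**2. Size of the spurious path.** With true B = 0, unit within-arm variances and one common cause acting in the same direction, the coefficient of outcome change on mediator change given arm is √(R²m × R²y). For equal shares this equals R².

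**3. Chance that it is significant.** With z = atanh(B) × √(137 − 4), the rejection rate is Φ(z − 1.96) + Φ(−z − 1.96). For B = .10, z = 0.1003 × 11.53 = 1.157 and the rate is 21%. Simulation used child-level change scores with A = 1.21, D = 0.43 and true B = 0:

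| Shared R² | Spurious B | Formula | Simulated, A×B alone | Simulated, A×B and D both significant |
|---|---|---|---|---|
| 5% | .05 | 9% | 8–10% | 2% |
| 10% | .10 | 21% | 20–22% | 2–3% |
| 15% | .15 | 41% | 42–43% | 5% |
| 20% | .20 | 65% | 65–67% | 6% |
| 25% | .25 | 84% | 83–85% | 6% |

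Ranges are across repeated runs. With severity in both equations, A×B returns to about 5% throughout. At R² = 25% the spurious B exceeds the plan's detectable .237.

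**4. Variations.**
- Unequal shares (mediator/outcome): 20%/5% gives B = √(.20 × .05) = .10 and 21–22%; 20%/2% gives B = .063 and 11–12%; 10%/2% gives B = .045 and 8%.
- Opposite directions: the sign of the spurious B reverses.
- Change-score reliability of .7: 6/13/23/39/52% in place of the A×B column.
- D = 0.64 with both paths required: 10% at R² = 10% and 27% at R² = 20%.
- Two causes, each with loading .32 on both changes (10% each), N = 140: spurious B = 2 × .32² = .20 (simulated .21), and the path from problem solving to global development is significant in 68%. Adjusting for only one of the two leaves 27%.

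**5. The comparison with D.** The spurious indirect effect is taken out of D: D = 0.43 − 1.21 × B. For B = .10 the indirect effect is .12 and D is .31. For B = .25 they are .30 and .13, so .30/.43 ≈ 70% of the effect looks mediated when none is.

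**The case against.** The strongest reply is that section ix does not rest on A×B alone. It expects D to remain significant too, and because a spurious B is subtracted from D, the joint condition holds false declarations to about 2–6% at D = 0.43. This stands, and it means the 8–84% range must not be read as the plan's false-declaration rate. It does not dispose of the point. Section ii words the hypothesis as mediation that is at least partial, which could be read as needing only the indirect effect. The joint rate rises to 10–27% at D = 0.64. The value 0.43 was derived for the intervention period, not follow-up. And the indirect-to-direct comparison is distorted whichever rule is used.

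Other replies also have weight:
- Mediator and outcome change fall in different phases, so equal shares are not established. Unequal shares gave 8–22%.
- A reader might infer that milder infants gain more on every measure. No passage gives a direction.
- A reader might take Secondary Hypothesis 2 as stating a medium-sized main effect of home environment. It sits under the moderator heading and may mean moderation. Secondary Hypothesis 1 refers to overall change and does support a main effect.
- A reader might conclude that covariates were left out of the model. The figure is not shown and the drawn model is simplified, so the documents support only that none is stated. Carrying the covariates over from the Hypothesis 1 and 2 equation as printed would adjust levels, not the slopes that form B, C1 and C2.

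The r = .32 baseline correlation in section iv is a power assumption, not adjustment. The moderator analyses are separate models for each outcome and do not alter the SEM.

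**Conclusion.** The point holds for the model as described. Neither randomisation nor temporal order protects B, C1 or C2, the SAP itself predicts a baseline influence on both sides of those paths, and D cannot absorb it. The indirect effects and their comparison with D are therefore biased, by an amount and in a direction the documents do not settle.

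The numerical range depends on the assumed shares, on direction, on change scores standing in for the full latent growth model, and on which decision rule applies. A weak common cause does little harm; a strong shared one can produce a path as large as the plan is powered to detect. The randomised comparisons in Hypotheses 1 and 2 are not affected.

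**What to change.** In SAP section ix, Evaluation of Primary Hypotheses 3 & 4:

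1. Regress the mediator RX slopes and the Bayley change factor on baseline severity (the 4–12 total), age at entry and site, and on SES, HOME and PCI-DMC as measured at baseline. Let the baseline (intercept) factors predict the slopes. Using only three severity categories left 8.3% false significance at R² = 20%. The assessment schedule does not show when HOME and PCI-DMC are taken, so state that baseline values are used.
2. Leave out fidelity, which arises after randomisation.
3. Keep the set short, severity first. Five covariates plus three site contrasts on four slopes is 8 × 4 = 32 paths, with about 140 infants.
4. Add a sensitivity analysis that fixes the residual mediator-outcome correlation over a grid (for example 0 to .3) and reports where the indirect effect vanishes.
5. State whether support for mediation requires D to be significant as well as the indirect effect.
6. Replace the claim of strong inference with a statement that B, C1 and C2 are observational and assume no unmeasured mediator-outcome confounding. Delete the statement that other factors are represented by D.

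Cost: no added participants, but more SEM parameters and a more qualified mediation claim. Power for a true B of .237 fell from 77% (no confounder, unadjusted) to 75% (adjusted, severity explaining 20%) when severity alone was added; the full set would probably cost more. The return to about 5% assumes that severity is the only confounder and is measured without error, which is why the sensitivity analysis is needed as well.
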